### **5 STATISTICAL ANALYSES**

#### **5.1 General Considerations**

Statistical analysis and generation of tables, figures, subject data listings, and statistical outputs are performed using SAS version 9.3 or higher. Calculations of PK parameters are made with Phoenix® WinNonlin® version 8.2 or higher. All tables and listings use Courier New font size 9.

Descriptive statistics are displayed to provide an overview of the study results. For categorical parameters, the number and percentage of participants in each category are presented. The denominator for percentages is based on the number of participants appropriate for the purpose

of analysis. Unless otherwise noted, all percentages are displayed to 1 decimal place. No percentage is displayed for zero counts, and no decimals are presented when the percentage is 100%. For continuous parameters, descriptive statistics include number of participants/observations with available measurements (n), mean, standard deviation (SD), median, minimum, and maximum unless otherwise specified.

For decimal places for descriptive statistics, the following rules are applied unless otherwise stated:

- “n” is an integer.
- (Arithmetic or geometric) mean, SD, and median use 1 additional decimal place compared to the original data.
- Minimum and maximum have the same number of decimal places as the original value.
- Coefficient of variance (CV) [%] is presented with 1 decimal place.
- Confidence interval (CI) has the same number of decimal place as the corresponding point estimate.

A set of data listings containing all documented data and all calculated data (eg, change from Baseline) is to be provided.

### **5.1.1 General study level definitions**

#### **5.1.1.1 Analysis Time Points**

##### **5.1.1.1.1 Relative day**

Relative day is calculated as the current date minus the date of first dose of IMP for days prior to the first dose of IMP, and the current date minus the date of first dose of IMP plus 1 for days on or after the first dose of IMP (eg, the day of first dose is Day 1 and the day prior to first dose is Day -1). Day 1 is composed of predose and postdose portions. Relative day is not calculated for partial dates, which will be presented as ‘--’ in the relevant participants data listing.

##### **5.1.1.1.2 End date of the Treatment Period**

The end date of the Treatment Period (ie, Single-Dose Period + Multi-Dose Period) is either the date of Day 13 for participants completing the Treatment Period, or the date of the withdrawal for participants who discontinue during the Treatment Period.

##### **5.1.1.1.3 Study periods and visits**

The following study periods/visits are defined for the classification by study period/visits:

- Screening Visit: Day -28 to Day -2
- Treatment Period: Day -1 to Day 13 (14 in-house days)
- Single-Dose Period: Day -1 to Day 4
- Multiple-Dose Period: Day 5 to Day 13
- SFU Visit: Day 15 (2 days after discharge)

#### **5.1.1.4      Definition of Baseline values**

Baseline for safety outcomes (ie, laboratory variables [blood chemistry, hematology, urinalysis], vital signs, and body weight) is defined as the last non-missing value prior to the first dose of IMP.

Baseline should be determined separately for each individual laboratory variable and each individual vital sign variable. An exception is blood pressure, where a complete set of both systolic and diastolic blood pressure should be selected from the same assessment for Baseline.

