### 4.3.2 Other safety variables

- Changes in vital signs (SBP, DBP, pulse rate, respiratory rate, and body temperature)
- Standard 12-lead ECGs parameters and findings
- Changes in clinical laboratory test parameters (hematology, blood chemistry, and urinalysis)

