## **8.3 Day 1**

The following procedures will be performed predose:

- Perform 12-lead ECG (if not performed on Day -1, 3 ECGs will be performed at 15min [ $\pm 5$ min] intervals within 24h before dosing of BRV on Day 1)
- Obtain blood samples for safety laboratory assessments and plasma PK

- Study drug administration (after all predose assessments are completed)

The following procedures will be performed postdose:

- Obtain vital sign measurements (SBP, DBP, pulse rate, respiratory rate, and body temperature) at 1, 2, and 4h postdose. A window of  $\pm 15\text{min}$  is allowed.
- Perform 12-lead ECG at 1, 2, and 4h postdose. A window of  $\pm 15\text{min}$  is allowed.
- Obtain blood samples for plasma PK at 0.25, 0.5, 1, 1.5, 2, 3, 4, 6, 9, and 12h postdose
- Record concomitant medication and medical procedures
- Record AEs

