### **10.3.3 Vital signs**

At time points specified in [Table 5–2](#) and [Table 5–3](#), SBP, DBP, pulse rate, respiratory rate, and body temperature in supine and standing positions will be recorded at supine rest (at least 5 minutes) and 1 minute after standing.

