### **12.4.3 Vital signs and ECG**

Vital sign variables and changes from Baseline will be descriptively summarized at each time point.

Electrocardiogram parameters (RR interval, PR interval, QRS interval, QT, corrected interval between Q and T waves on ECG [Bazett's Formula Correction], and corrected interval between Q and T Waves on ECG [Fridericia Correction]) and change from Baseline will be descriptively summarized by scheduled time point. Hereby, Baseline is defined as the mean of triplicate measurements of the ECG parameters prior to the first dose of study drug.

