#### **5.6.3.2 Vital Signs**

The following parameters are measured:

- systolic blood pressure (SBP), diastolic blood pressure (DBP), pulse rate, respiratory rate, and body temperature.

Observed values for the vital sign parameters are summarized with descriptive statistics for the scheduled time points. Changes from Baseline (Day1-predose) for each parameter are summarized for all post-Baseline time points.

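### Do the unstated vital-sign position and the gap in the Day 1 predose list leave change from Baseline undefined?

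*SAP*

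**What the plan says.** Protocol 10.3.3 covers the time points in Tables 5-2 and 5-3. It has the five vital signs measured twice: "in supine and standing positions will be recorded at supine rest (at least 5 minutes) and 1 minute after standing".

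The analysis sections name no position:

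- Protocol 4.3.2 lists the variable as "Changes in vital signs (SBP, DBP, pulse rate, respiratory rate, and body temperature" and stops there.
- Protocol 12.4.3: "Vital sign variables and changes from Baseline will be descriptively summarized at each time point".
- SAP, Definition of Baseline values: Baseline "is defined as the last non-missing value prior to the first dose of IMP". It continues: "Baseline should be determined separately for each individual laboratory variable and each individual vital sign variable". For blood pressure, "a complete set of both systolic and diastolic blood pressure should be selected from the same assessment for Baseline".
- SAP 5.6.3.2: "Changes from Baseline (Day1-predose) for each parameter are summarized for all post-Baseline time points".

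On Day 1, Protocol Tables 5-1 and 5-2 and SAP Table 1-2 all schedule predose vital signs. The predose list in Protocol 8.3 has the ECG, the instruction "Obtain blood samples for safety laboratory assessments and plasma PK", and then dosing. Vital signs appear in that section only after the dose. The predose lists for Day 7 (8.9) and Day 10 (8.12) do include them.

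**The concern.** A rule that takes the last value before dosing assumes one value per time point. With a supine and a standing reading, it would return the standing one if the two are timed separately, and could not choose if they share a time. The rule also governs Baseline only; nothing states which position supplies each later value. If the positions were mixed, the ordinary response to standing up would enter the change from Baseline and could be read as a drug effect, or hide one.

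The gap in 8.3 raises a second worry. A site working from that list alone would take no vital signs before the first dose. The Day -1 list (8.2) has none either, so the last reading would be from Screening, 28 to 2 days before Day 1. The SAP's general Baseline rule would accept it, but the Day 1 predose label in SAP 5.6.3.2 would then be wrong.

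**Working it through.** The plan gives no figure to reproduce here. The check is a count and a comparison of sections.

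**Time points and series**

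- Table 5-2: predose, 1, 2, 4 and 72h = 5.
- Table 5-3: Day 7 predose; Day 10 predose, 1, 2, 4 and 72h = 6.
- Time points with two positions: 5 + 6 = 11.
- Post-Baseline: 11 − 1 (Day 1 predose) = 10, plus the Day 15 follow-up = 11.
- Series: 5 parameters × 2 positions = 10.

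**What mixing positions would do**

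Let the within-position change be d and the standing-minus-supine difference be p. A standing value minus a supine Baseline gives d + p; with no drug effect, d = 0 and the result is p. The documents give no value for p, so no bias can be sized. The shift arises only if Baseline and the later value come from different positions.

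**Does the plan lead there?**

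1. A reading required in each of two positions cannot be recorded as required without marking the position. Supine and standing systolic pressure then arrive as distinguishable data.
2. The SAP sets Baseline separately for each vital-sign variable. Once position is part of the variable, the last-value rule gives one supine and one standing Baseline, and change is taken within each.
3. Both blood pressures must come from one assessment, so on its natural reading the rule does not allow a supine systolic Baseline with a standing diastolic one.
4. If the positions were pooled without selection, a time point with 12 subjects would show 12 × 2 = 24 observations, which would be seen in the first draft table. If the last-value convention were instead carried to every time point in the two tables, the comparison would be standing with standing.

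No section says that the positions are pooled into one variable, and a cross-position change needs that step.

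**Day 1 predose reading**

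| Source | Vital signs before the first dose? |
|---|---|
| Protocol Table 5-1 | Yes |
| Protocol Table 5-2 | Yes |
| Protocol 10.3.3 | Yes, by pointing to Table 5-2 |
| SAP Table 1-2 | Yes |
| SAP 5.6.3.2 | Yes, as the Baseline label |
| Protocol 8.3 list | Omitted |

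Section 8.3 itself holds the dose until every predose assessment is finished. The omission is one list against five consistent statements.

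**The case for a change.** The strongest reply is that the SAP does settle the matter for ECGs: it averages the triplicate predose tracings and says what to do if fewer are available. SAP Amendment 1 even revised that definition to match the protocol. Vital signs get no such rule, the words supine and standing are absent from the SAP, and the case report form that would show how positions are stored is not among the documents. The Day 15 visit lies outside Tables 5-2 and 5-3, so its position is stated nowhere. Protocol 10.3.3 may itself be the odd one out, since the other sections that define or analyse vital signs are silent on position.

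The textual mismatch stands, and so does the Day 15 point, which affects 1 of the 11 post-Baseline time points. The ECG comparison carries less weight. Triplicate tracings are repeats of one quantity and need a rule for combining them; supine and standing pressures are different quantities and need only be kept apart. The unseen case report form cuts both ways: it prevents proof that positions are separated, but the protocol's own collection instruction makes separation the expected outcome. At Day 15 an analyst can match the recorded position to the same Baseline, or list the value if the position is unknown.

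**Conclusion.** No change to the plan is needed. The position point is missing detail that an analyst would fill by comparing like with like, and the SAP's variable-by-variable Baseline already supports that reading. The gap in Protocol 8.3 is a clerical slip that the schedule tables correct.

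The reach is small: descriptive summaries of an other-safety variable in 12 subjects, with no hypothesis test and with the documented data listed. The pharmacokinetic endpoints and the incidence of treatment-emergent adverse events do not depend on it. Spelling out the position would make the text tidier without altering a result or a conclusion.

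This rests on two assumptions: that position is recorded with each reading, as 10.3.3 implies, and that the site works from the schedule tables. If the second failed, the general Baseline rule would fall back on the Screening reading. For blood pressure and pulse that reading is supine, because inclusion criterion 7 is assessed in that position; the documents do not promise a standing value at Screening.

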#### **5.1.1.2      Protocol Deviations**

Important protocol deviations (IPDs) are deviations from the protocol which potentially could have a meaningful impact on the key safety or PK outcomes or on study conduct for an individual subject.

The criteria for identifying important protocol deviations and the classification of important protocol deviations are defined within the protocol-specific document, Specification of Protocol Deviations (SPD). To the extent feasible, rules for identifying protocol deviations are defined without review of the data and without consideration of the frequency of occurrence of such deviations. They are identified from various sources such as programmed edit checks, programmed listings, and monitoring reports, and finalized in the SPD during the Data Evaluation Meeting (DEM) prior to database lock.

Any samples that are obtained outside the tolerance window permitted at the specified timepoint will be discussed at the DEM and any possible exclusion from analysis will be documented accordingly.

The categories (eg, inclusion/exclusion criteria, withdrawal criteria, Prohibited concomitant medication use, treatment/procedure non compliance, and incorrect treatment or dose) are not fixed and can be adapted, extended, or reduced according to the needs of the study.

#### *Time deviation of blood sampling for determination of PK parameters*

Unless otherwise indicated, any sample taken earlier or later than scheduled is considered a time deviation even if the deviation is pharmacokinetically irrelevant.

The maximum deviations from scheduled sampling times for PK are defined as follows:

- 0h (predose): within 30min before dosing
- 0.25h:  $\pm 1$ min
- 0.5h:  $\pm 2$ min
- 1 to 4h:  $\pm 3$ min
- 6 to 9h:  $\pm 6$ min
- 12 to 16h:  $\pm 12$ min
- $\geq 24$ h:  $\pm 20$ min

### **5.1.1.3 Treatment assignment and treatment groups**

As this is a single-arm study, data are summarized only as a whole.

### **5.1.1.4 Center pooling strategy**

As this is a single-center study, pooling of centers is not applicable.

### **5.1.1.5 Coding dictionaries**

Medical history and AEs are coded using the Medical Dictionary for Regulatory Activities (MedDRA) version 18.1. Medications are be coded using the World Health Organization Drug Reference List (WHO-DRL) 201709(B3 format). Medical procedures are not coded.

## **5.2 Participant Dispositions**

A study participant is considered to have completed the study if all periods of the study have been completed, including the last scheduled procedure shown in the Schedule of activities in the protocol.

The number of participants screened and screen failures and the primary reason for screen failure are summarized for all participants screened (ES).

The number and percentage of participants who started study (will be defined as participants with dose), participants who completed or prematurely discontinued the study, as well as the reason for discontinuation will be summarized based on the SS.

The number and percentage of participants who discontinued due to AEs will be separately summarized based on the SS.

The following listings will be presented:

- Participants who did not meet study eligibility criteria (ES)
- Participants disposition (ES)
- Study discontinuation (SS)
- Visit dates (SS)
- Participants analysis sets (ES)

The listing of participant disposition will include the date of informed consent, date and time of first and last dose of IMP, date of premature termination and primary reason (if applicable), and date of final contact.

The listing of study discontinuation will include the reason for discontinuation and the number of days on IMP.

The number of days on IMP will be calculated as the actual days that the participant received at least one dose of IMP.

## **5.3 Primary Endpoint(s) Analysis**

The primary analysis for this study is the PK analysis, outlined in Section 5.7.1.1.

## **5.4 Secondary Endpoint(s) Analysis**

The secondary analysis for this study is the safety analysis, outlined in Section 5.6.

## **5.5 Tertiary/Exploratory Endpoint(s) Analysis**

Not applicable.

## **5.6 Safety Analyses**

All safety analyses are conducted for the SS. Safety measurements are summarized at each scheduled time point.

### **5.6.1 Extent of Exposure**

All IMP administration details including actual date-time at dosing and dose will be listed by dose period and participant.

### **5.6.2 Adverse Events**

Adverse events are coded using the MedDRA and are classified as either pre-treatment or treatment- emergent. Pre-treatment AEs are defined as AEs which have onset prior to the first dose of IMP. Treatment-emergent adverse events (TEAEs) are defined as AEs which have onset or worsening severity (relative to pre-treatment) after the first dose of IMP.

Summaries of TEAEs will include the following:

- Incidence of TEAEs - overview (including number and percentage of participants with any TEAEs, serious TEAEs, discontinuations due to TEAEs, drug-related TEAEs, severe TEAEs, TEAEs leading to death, TEAE of special interest, and TEAE related to COVID-19 vaccination; event counts will also be included)
- Incidence of TEAEs
- Incidence of serious TEAEs
- Incidence of TEAEs of special interest
- Incidence of TEAEs by maximum relationship
- Incidence of TEAEs by maximum intensity
- Incidence of TEAEs leading to discontinuation by relationship

---

- Incidence of fatal TEAEs by relationship
- Incidence of serious TEAEs by relationship
- Incidence of non-serious TEAEs above reporting threshold of 5% of participants
- Incidence of TEAEs related to COVID-19 vaccination

For overview of TEAE and incidence of TEAE tables, AEs will be attributed to the dose period in which they start. Thus, all AEs starting after the first intake of BRV and before the intake of Day 5 will be attributed to Single-Dose Period; all AEs starting after BRV intake on Day 5 and on or before Day 13 will be attributed to the Multiple-Dose Period and AEs starting on or after Day 14 will be attributed to the SFU period.

The number and percentage of participants who experience TEAEs will be summarized by MedDRA SOC and PT. Only overview of TEAE and incidence of TEAE tables will be presented by dose period (Single-Dose, Multiple-Dose, and SFU period) and overall. Other TEAE tables will only be presented overall results.

Summary tables will contain counts of study participants, percentages of study participants in parentheses and the number of events where applicable. A participant who has multiple events in the same SOC or PT will be counted only once in the participant counts but all events will be included.

In summaries including relationship, the following relationships will be summarized: ‘Not related’, ‘Related’. Participants who experience the same event multiple times will be included in the most related category for tabulations by maximum relationship. Events with missing relationship will be considered as ‘Related’ for summary purpose but recorded as missing in the listings.

In summaries including intensity, the following intensity categories will be summarized: ‘Mild’, ‘Moderate’, ‘Severe’. Participants who experience the same event multiple times will be included in the most severe category for tabulations by maximum intensity. Events with missing intensity will be considered as ‘Severe’ events for summary purposes but recorded as missing in the listings.

Adverse event summaries will be ordered alphabetically by SOC and decreasing frequency of PT within SOC.

A listing for all AEs will be presented by participant and will include the onset date/time and outcome date/time of the event (including relative days), the AE duration (derived), pattern of event, intensity, relationship, action taken and outcome.

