## **8.16 Safety Follow-Up Visit**

The subject will return to the clinic 2 days later (Day 15) for the SFU Visit. The following procedures will be performed:

- Perform physical examination
- Assess C-SSRS
- Obtain vital signs
- Perform 12-lead ECG
- Record concomitant medication and medical procedures
- Record AEs

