#### **10.1.2.3 Additional procedures for reporting serious adverse events**

If an SAE is reported, UCB must be informed within 24 hours of receipt of this information by the site (see contact information for SAE reporting listed in the Serious Adverse Event Reporting section at the front of the protocol). The Investigator must forward to UCB (or its representative) a duly completed “Investigator SAE Report Form for Development Drug” (SAE report form) provided by UCB, even if the data are incomplete, or if it is obvious that more data will be needed in order to draw any conclusions. Information recorded on this form will be entered into the global safety database.

An Investigator SAE report form will be provided to the Investigator. The Investigator SAE Report form must be completed in English.

It is important for the Investigator, when completing the SAE report form, to include the assessment as to a causal relationship between the SAE and the IMP administration. This insight from the Investigator is very important for UCB to consider in assessing the safety of the IMP and in determining whether the SAE requires reporting to the regulatory authorities in an expedited manner.

Additional information (eg, autopsy or laboratory reports) received by the Investigator must be provided within 24 hours. All documents in the local language must be accompanied by a

translation in English, or the relevant information included in the same document must be summarized in the Investigator SAE report form.

The Investigator is specifically requested to collect and report to UCB (or its representative) any SAEs (even if the Investigator is certain that they are in no way associated with the IMP), up to 30 days from the end of the study for each subject, and to also inform participating subjects of the need to inform the Investigator of any SAE within this period. Serious AEs that the Investigator thinks may be associated with the IMP must be reported to UCB regardless of the time between the event and the end of the study.

Upon receipt of the SAE report form, UCB will perform an assessment of expectedness of the reported SAE. The assessment of the expectedness of the SAE is based on the Investigator's Brochure.

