**Table 1–1: Objectives and Endpoints**

Objectives	Endpoints
	
Primary Safety Endpoints:
 
 
• Incidence of treatment-emergent AEs (TEAEs)
 
 
Other Safety Endpoints:
 
 
• Changes in vital signs (SBP, DBP, pulse rate, respiratory rate, and body temperature)
 
• Standard 12-lead ECGs parameters and findings
 
• Changes in clinical laboratory test parameters (hematology, blood chemistry, and urinalysis)
 

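### The by-period TEAE tables set windows of about 4.0, 8.7 and 1.5 days side by side with no measure of time at risk and no stated N per period

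*SAP*

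**What the plan says.** The primary safety endpoint in SAP Table 1–1 is the incidence of TEAEs, with no split by period. SAP 5.6.2 plans the tables as follows: "Only overview of TEAE and incidence of TEAE tables will be presented by dose period (Single-Dose, Multiple-Dose, and SFU period) and overall". All other TEAE tables are overall only, so these two are the only planned TEAE display that sets single against repeated dosing.

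Each event goes to the period in which it starts:

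- Single-Dose: "all AEs starting after the first intake of BRV and before the intake of Day 5 will be attributed to Single-Dose Period".
- Multiple-Dose: "all AEs starting after BRV intake on Day 5 and on or before Day 13 will be attributed to the Multiple-Dose Period".
- SFU: "AEs starting on or after Day 14 will be attributed to the SFU period". No end is given.

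On who is counted, SAP 5.6 says "All safety analyses are conducted for the SS", and SAP 4.2 admits anyone with at least one dose. SAP 5.1 adds only that percentage denominators are whatever number of participants suits the analysis. SAP 6.1.5.1 and Protocol 12.6 provide for replacing participants who drop out for non-safety reasons.

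On follow-up, Protocol 8.16 says "The subject will return to the clinic 2 days later (Day 15) for the SFU Visit". Protocol 10.1.2.3 asks for SAEs to be collected and reported "up to 30 days from the end of the study for each subject".

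The tables show participant counts, percentages and event counts. SAP 5.6.1 plans a listing of dosing details, but no summary of time at risk.

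**The concern.** Both a cumulative percentage and an event count grow with the length of observation. The three columns cover very different lengths, and nothing in the tables tells the reader so. The study has a single arm, so no placebo column would show how many events the unit's background rate produces in each window. The objective is safety and tolerability after a single dose and after multiple doses. A reader will therefore compare the first two columns, and could take a difference due to longer observation for an effect of repeated dosing.

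Two smaller gaps affect the same tables. If the Safety Set is the denominator throughout, someone who left before Day 5 still counts in the later columns, where they could not contribute an event. And with no closing rule for the SFU column, two programmers could cut it at different points.

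**Working it through.** **The plan's own figures.** The stated maximum duration of 43 days reproduces as 28 + 13 + 2. The 12 scheduled doses in SAP 6.1.7 reproduce as 1 + 5 × 2 + 1, that is 1 in the Single-Dose Period and 11 in the Multiple-Dose Period. The plan has no power calculation and gives no TEAE rate to reproduce.

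**Windows**, from the attribution rule in SAP 5.6.2. Clock times are assumptions: dosing at 08:00, SFU visit at noon.

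- Single-Dose: Day 1 08:00 to Day 5 08:00 = 4.00 days.
- Multiple-Dose: Day 5 08:00 to the end of Day 13 = 8 + 16/24 = 8.67 days. Dosing between 07:00 and 10:00 gives 8.71 to 8.58.
- SFU: Day 14 00:00 to Day 15 noon = 1.50 days. A visit between 08:00 and 18:00 gives 1.33 to 1.75.

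The ratio of Multiple-Dose to Single-Dose is 8.67/4.00 = 2.17 (2.15 to 2.18 over the dosing times above). For 12 participants the participant-days are 12 × 4 = 48, 12 × 8.67 = 104 and 12 × 1.5 = 18.

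**Expected event counts.** At a constant background rate per participant-day, the expected count is rate × participant-days. The Multiple-Dose to Single-Dose ratio is 104/48 = 2.17, whatever the rate.

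**Expected percentages.** For an assumed Single-Dose incidence p, the daily hazard is λ = −ln(1 − p)/4, and incidence over d days is 1 − exp(−λd).

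| Single-Dose (assumed) | Multiple-Dose, 8.67 d | Ratio to Single-Dose | SFU, 1.5 d |
|---|---|---|---|
| 5% | 10.5% | 2.10 | 1.9% |
| 10% | 20.4% | 2.04 | 3.9% |
| 20% | 38.3% | 1.92 | 8.0% |
| 30% | 53.8% | 1.79 | 12.5% |
| 50% | 77.7% | 1.55 | 22.9% |
| 70% | 92.6% | 1.32 | 36.3% |

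The ratio reaches 1.8 only when Single-Dose incidence is about 30% or less.

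**What a rate would show.** At 10% Single-Dose incidence, λ = −ln(0.9)/4 = 0.026 per day. Events per participant-day then have the same expected value, 0.026, in all three columns, where the percentages read 10.0%, 20.4% and 3.9%.

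**How the windows differ apart from length.** The time after the last dose is similar in the two dosing periods: 4.0 days, against 3.67 days from Day 10 08:00 to the end of Day 13. The extra 8.67 − 3.67 = 5.0 days in Multiple-Dose are the days of repeat dosing. Day 14 begins 88 h after the last dose. At the stated half-life of about 9 h that is 88/9 = 9.8 half-lives.

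**Denominator.** Suppose 12 participants are dosed from Day 5 and 4 have a TEAE in the Multiple-Dose Period. The percentage is 4/12 = 33.3% of those dosed in the period. If one earlier dropout was replaced, the Safety Set is 13 and the figure is 4/13 = 30.8%. With two replaced it is 4/14 = 28.6%. Without replacement, if 2 of 12 leave before Day 5 and 3 are affected, it is 3/10 = 30.0% against 3/12 = 25.0%.

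**The case against.** The strongest reply is that the tables are descriptive. The overall column reports the primary safety endpoint as defined, and no test between periods is planned. The extra time in Multiple-Dose is essentially the repeat dosing that the objective asks about, so cumulative incidence per regimen is a legitimate quantity. With 12 participants, the listings of dosing times (SAP 5.6.1) and AE onset times (SAP 5.6.2) let a reader recompute anything. All of this stands, and it limits the point to how two tables are presented. It does not make the columns comparable: a raw percentage still mixes longer observation with more doses, and the tables give the reader no warning.

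On the denominator, the reply is that SAP 5.1 permits a period-specific N and that participants are confined until Day 13. The text does permit that reading, but it does not require it, and SAP 5.6 points to the Safety Set. The choice matters only if someone leaves early.

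A reader might infer that the SFU column will hold about a month of SAEs beside about 1.5 days of other AEs. The documents do not establish this. Protocol 10.1.2.3 sets a reporting duty and sends the form's content to the global safety database. Nothing says that SAEs with onset after a participant's last visit enter the TEAE tables. What stands is that the column has no stated end.

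**Conclusion.** The columns of the two by-period tables are not on a comparable time basis, and neither the N per period nor the end of the SFU column is fixed. Under a constant background rate with no drug effect, expected event counts would be about 2.2 times higher in Multiple-Dose than in Single-Dose. Percentages would be about 2.0 times higher at 10% Single-Dose incidence, 1.8 times at 30% and 1.55 times at 50%. These sizes rest on the constant rate and on assumed clock times. The denominator effect rests on early departures that may not happen.

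A reader might go further and say that TEAE incidence doubles and then falls by construction, or that the primary safety endpoint is distorted. The documents support neither. Near-doubling of percentages needs both a constant rate and a fairly low Single-Dose incidence. Part of any real rise may come from repeat dosing. A lower SFU column is also expected from washout, and any late SAE counted there would work against a fall. The overall column is untouched. This is a cheap improvement to the tables, not an error in the main safety estimate.

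**What to change.** In SAP 5.6.2, for the by-period TEAE overview and incidence tables:

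- (a) Use as denominator the participants dosed in that period (for SFU, those observed on or after Day 14), and print that N in the column header.
- (b) Add participant-days of observation and TEAEs per participant-day under each column.
- (c) Close the SFU column at the SFU visit, and list any SAE with later onset separately.

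The cost is SAP wording and a few derived rows. Dosing times, AE onset times and visit dates are already planned for the listings. One limitation needs a footnote: the Multiple-Dose rate averages dosing days and the washout after Day 10, so an equal rate does not prove an equal risk on dosing days.

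A matched line giving incidence over the 96 h from the Day 5 dose is optional. It would set 8 of the 11 repeat doses beside one dose plus its washout, so it matches time but not dosing.
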